9.7.1.5.1. Primary Efficacy Analysis

Primary Estimands: The primary estimands are the treatment differences between SY-201 Ophthalmic Solution arms and vehicle for mean CFB to Day 60 in tCFS using study eyes and mean CFB to Day 60 in eye [REDACTED] using the FAS.

Target Population: Subjects with DED who meet the study entry criteria.

Endpoints: Change from baseline at Day 60 for tCFS using study eyes and change from baseline at Day 60 for eye dryness score.

Treatment Condition(s): Treatment condition is based on the randomized treatment group.

Population-level Summaries: The difference in the mean CFB to Day 60 in tCFS using study eyes and the difference in mean CFB to Day 60 in eye dryness score and their p-values and corresponding 95% confidence intervals.

The proposed procedures to handle missing data and intercurrent events are as follows:

- Discontinuation of study therapy with continued participation in the study
 - Treatment Policy – no imputation; use observed data
- Receipt of rescue therapy
 - Treatment Policy – no imputation; use observed data
- Missing data with or without withdrawal, regardless of reason
 - Hypothetical approach – missing data will be accounted for assuming missing at random (MAR) using mixed-model repeated measures (MMRM).

Mean CFB in tCFS will be analyzed using a MMRM model. The model will include the baseline measurement, treatment, time, and treatment by time interaction as fixed effects, with a random effect for site. An unstructured covariance among repeated measurements is assumed. A similar model for the subject-level mean CFB in eye dryness score will be used.

Sample repeated measures model code:

```
PROC MIXED DATA=indata;
  CLASS subject center visit treatment(REF='Vehicle');
  MODEL change = baseline_value visit treatment visit*treatment / Solution DDFM=KR;
  REPEAT visit / SUBJECT=subject TYPE=UN;
```

```
RANDOM center;
LSMEANS treatment*visit / slice = visit DIFF CL;
RUN;
```

If the model fails to converge using this covariance structure, spatial power or compound symmetry will be implemented in this order.

Sensitivity analyses of the primary endpoints will be performed utilizing control-based pattern imputation, last observation carried forward (LOCF), and baseline observation carried forward (BOCF).

Control-based pattern imputation would be performed using code similar to the below. The first call is to ensure a monotone missing data pattern. The second call is to perform the control-based pattern imputation.

```
PROC MI DATA=indata SEED= OUT=monotone MINIMUM=0 0 0 0 0 MAXIMUM=4 4 4 4 4 ROUND=0.5
NIMPUTE=25;
  MCMC IMPUTE = MONOTONE;
  VAR value_V2 value_V3 value_V4 value_V5 value_V6;
RUN;

PROC MI DATA=monotone SEED= OUT= MINIMUM=. 0 0 0 0 0 MAXIMUM=. 4 4 4 4 4 ROUND=0.5
NIMPUTE=1;
  by _imputation_;
  CLASS treatment;
  VAR value_V2 value_V3 value_V4 value_V5 value_V6;
  MONOTONE reg(/details);
  MNAR model(value_V3 value_V4 value_V5 value_V6 / modelobs= (treatment = 'vehicle'));
RUN;
```

Comparisons among individual arms will be obtained from the lsmeans statement. Comparisons between the combined SY-201 arm and Vehicle (least-squares means, treatment differences, 95% confidence intervals, and p-values) will be obtained using estimate statements. Assume treatments are ordered:

1. SY-201 2.0%;
2. SY-201 1.0%;
3. SY-201 0.5%;
4. Vehicle.

And visits 3, 4, 5, and 6 are ordered numerically. Let $n_{2.0\%}$, $n_{1.0\%}$, and $n_{0.5\%}$ be the total number of subjects for the appropriate arms in the respective analysis set (FAS or Per Protocol). Define

$$p_{2.0} = \frac{n_{2.0\%}}{n_{2.0\%} + n_{1.0\%} + n_{0.5\%}} \text{ with } p_{1.0} \text{ and } p_{0.5} \text{ defined similarly.}$$

To generate the estimates for the combined SY-201 for Visit 3, see the below code for an example for Visit 3.

```
estimate 'SY-201 Average V3'
  intercept      1
  baseline       <<overall average at baseline for all subjects>>
  visit          1 0 0 0
  treatment      p2.0 p1.0 p0.5 0
```

```
visit*treatment p2.0 p1.0 p0.5 0 0 0 0 0  
0 0 0 0 0 0 0 0;  
  
estimate 'SY-201 Average minus Vehicle V3'  
treatment p2.0 p1.0 p0.5 -1  
visit*treatment p2.0 p1.0 p0.5 -1 0 0 0 0  
0 0 0 0 0 0 0 0;
```

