9.4.2.1 Primary Efficacy Analyses

Primary Estimands: The primary estimands are the treatment differences between SY-201 Ophthalmic Solution arms and vehicle for mean CFB to Day 60 in tCFS using study eyes and mean CFB to Day 60 in [REDACTED] score using the FAS.

Target Population: Subjects with DED who meet the study entry criteria.

Treatment Condition(s): Treatment condition is based on the randomized treatment group.

Population-level Summaries: The difference in the mean CFB to Day 60 in tCFS using study eyes and the difference in mean CFB to Day 60 in [REDACTED] score and their p-values and corresponding 95% confidence intervals.

[figure not shown]
The proposed procedures to handle missing data and intercurrent events are as follows:

- Discontinuation of study therapy with continued participation in the study
 - Treatment Policy – no imputation; use observed data
- Receipt of rescue therapy
 - Treatment Policy – no imputation; use observed data
- Missing data with or without withdrawal, regardless of reason
 - Hypothetical approach – missing data will be accounted for assuming missing at random (MAR) using mixed-model repeated measures (MMRM).

Mean CFB in tCFS will be analyzed using an MMRM model. The model will include the baseline measurement, treatment, time, and treatment by time interaction as fixed effects, with a random effect for site. An unstructured covariance among repeated measurements is assumed. A similar model for the subject-level mean CFB in [REDACTED] score will be used.

Additional sensitivity analyses will be described in the SAP.

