For analysis of efficacy endpoints, longitudinal models will model the change from baseline of each endpoint as the dependent variable with the baseline measurement of the corresponding endpoint as a covariate and treatment group as the main effect. A random effect for site will be added to account for site-to-site variability.

Subgroups

Subgroup analyses will include testing of the mean CFB in tCFS,

Subgroup analyses by sex and age group (<65 years, ≥65 years) may also be performed.

Multiplicity

To control for type I error, comparisons will be made within each active dose level of SY-201 Ophthalmic Solution compared to Vehicle. In other words, the primary endpoints will be compared sequentially between SY-201 Ophthalmic Solution 2.0% and Vehicle, first testing tCFS and, if statistically significant, . Should both endpoints achieve statistical significance for the 2.0% dose, testing will proceed to Y-201 Ophthalmic Solution 1.0% versus Vehicle, first testing tCFS and, if statistically significant, . Should both endpoints achieve statistical significance for the 1.0% dose, testing will proceed to SY-201 Ophthalmic Solution 0.5% and Vehicle, first testing tCFS and, if statistically significant, . In other words, the first non-significant result in this testing hierarchy of six hypotheses will imply that subsequent tests are non-significant.

Missing Data and Outliers

Every attempt will be made to capture all study data. All analyses will utilize observed data only. Analysis of continuous efficacy endpoints using MMRM assumes missing at random (MAR). Sensitivity analyses of the primary endpoints will be performed utilizing control-based pattern imputation, last observation carried forward (LOCF), and baseline observation carried forward (BOCF).

Visit Windows

The nominal visits listed in the eCRF will be used in the summaries. In general, unscheduled visits will not be summarized in tables unless otherwise noted.

Missing Dates

Missing dates that occur for prior or concomitant medications or adverse events will be queried for a date. If no date is obtained, the following imputation rules will apply:

- For start dates, if the given year (or year-month) is the same as study drug administration, the start date will be imputed as study drug administration date; otherwise, missing month-day (or day) will be imputed as '01-01' (or '01').

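### The primary MMRM fits one baseline slope for all visits; if that slope changes over time, the Day 60 contrast could lose some precision that a baseline-by-visit term would recover cheaply

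*SAP*

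**What the plan says.** Protocol 9.4.2.1 and SAP 9.7.1.5.1 describe the same model. The SAP says: "The model will include the baseline measurement, treatment, time, and treatment by time interaction as fixed effects, with a random effect for site". The protocol says: "The model will include the baseline measurement, treatment, time, and treatment by time interaction as fixed effects", with site as a random effect. The SAP code matches: "MODEL change = baseline_value visit treatment visit*treatment / Solution DDFM=KR". The general covariate statement in SAP 9.7.1 also enters baseline once, "with the baseline measurement of the corresponding endpoint as a covariate and treatment group as the main effect". None of these places has a baseline-by-visit term.

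On covariance the SAP says "An unstructured covariance among repeated measurements is assumed". Four post-baseline visits enter the model ("And visits 3, 4, 5, and 6 are ordered numerically"). The estimand concerns the last of them only: "Change from baseline at Day 60 for tCFS using study eyes and change from baseline at Day 60 for eye dryness score". The listed sensitivity analyses (control-based imputation, LOCF, BOCF) change how missing data are handled. They do not add a visit-specific baseline term to the analysis model.

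**The concern.** Treatment is allowed a separate effect at each visit, but baseline is not. The shared slope is a weighted average over Days 7, 14, 28 and 60, and it equals the Day 60 slope only if the relation between baseline and change is constant over time. Day 60 is the visit furthest from baseline and the only one in the testing hierarchy. That hierarchy stops at the first non-significant result, so precision at the first Day 60 test governs everything after it.

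If the slopes differ, two things follow. The Day 60 residual variance is larger than with a Day 60 slope. A chance difference in baseline means between an active arm and vehicle is corrected by the wrong multiple.

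**Working it through.** **Inputs from the documents.** 45 evaluable subjects per arm; tCFS difference 2.0 with SD of change 3.0; symptom difference 1.5 with SD 2.4; unpaired t-test, two-sided 0.05 (SAP 9.7.2, Protocol 9.2). Four post-baseline visits, four arms, 200 subjects.

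**Inputs that must be assumed.** Baseline SD, correlations with baseline, and correlations between post-baseline visits. The documents give none of these.

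**Step 1: the plan's own power.** Noncentral t, 88 df.
- tCFS: 2.0 / (3.0 × √(2/45)) = 3.16, power 87.85% (stated 87.9%).
- Symptom: 1.5 / (2.4 × √(2/45)) = 2.96, power 83.45% (stated 83.5%).

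Both reproduce. They use the unadjusted SD of change, so they claim no gain from baseline adjustment under either model.

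**Step 2: formulas (complete data, site effect ignored).**
- Slope of change on baseline at visit v: β_v = ρ_v × (SD_v / SD_0) − 1.
- Shared slope: b = 1′S⁻¹β / 1′S⁻¹1, where S is the covariance of the four changes given baseline.
- Day 60 variance ratio (shared slope / visit-specific slopes): 1 + (β60 − b)² × SD_0² / residual variance at Day 60.
- Shift in the estimate for a baseline imbalance d: |β60 − b| × d.

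**Step 3: scaling to the plan's SD of 3.0.** With equal SDs at all visits, SD_0 = 3 / √(2(1 − ρ60)) and residual SD = SD_0 × √(1 − ρ60²). The SE at 45 per arm is the residual SD × √(2/45), multiplied by the square root of the ratio for the shared slope.

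| Assumed correlation with baseline, Visits 3 to 6 | SD_0 | β60 | b | Residual SD | Variance ratio | SE shared / by visit |
|---|---|---|---|---|---|---|
| Constant 0.5 | 3.00 | −0.50 | −0.50 | 2.598 | 1.00 | 0.548 / 0.548 |
| Slight decay, 0.65 to 0.50 | 3.00 | −0.50 | −0.396 | 2.598 | 1.01 | 0.552 / 0.548 |
| Moderate decay, 0.7 to 0.4 | 2.74 | −0.60 | −0.387 | 2.510 | 1.05 | 0.543 / 0.529 |
| Exponential in days, 0.30 at Day 60 | 2.54 | −0.70 | −0.229 | 2.419 | 1.24 | 0.569 / 0.510 |
| Rising: 0.40, 0.45, 0.50, 0.60 | 3.35 | −0.40 | −0.489 | 2.683 | 1.01 | 0.569 / 0.566 |

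The slight and moderate rows step evenly across visits and take the correlation between two post-baseline visits as the ratio of their correlations with baseline. The constant row uses 0.5 throughout. The rising row uses 0.50 to 0.60 between post-baseline visits.

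Worked example, moderate decay: (0.213 × 2.739)² / 2.510² = 0.340 / 6.300 = 0.054, so the ratio is 1.054. That is worth 45 × 0.054 / 1.054 = 2.3 subjects per arm. For the exponential case: (0.471 × 2.535)² / 2.419² = 1.426 / 5.852 = 0.244, worth 45 × 0.244 / 1.244 = 8.8 subjects.

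Other assumed correlations between post-baseline visits move these figures. Moderate decay gives about 4 to 8%. A fall from 0.8 to 0.35 gives 14 to 28%. The top of the range reflects the structures tried and is not a bound.

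**Step 4: baseline imbalance.** For an assumed chance imbalance of 0.5 units, the moderate case leaves 0.213 × 0.5 = 0.11 units uncorrected and the exponential case 0.471 × 0.5 = 0.24. The rising case over-corrects by 0.089 × 0.5 = 0.04.

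**Step 5: simulation.** 200 subjects, unstructured covariance, about 10% monotone dropout, no treatment effect, no site effect.
- Exponential decay, 4,000 runs: rejection 4.5% (shared) and 4.8% (by visit); mean estimates 0.012 and 0.009; model SEs 0.567 and 0.507 against empirical 0.556 and 0.502.
- A decay structure with a variance ratio of 1.03, 3,000 runs: rejection 5.2% and 5.4%; mean estimates −0.001 under both.
- Equal slopes, 600 runs: mean model SE 0.545 without the extra term and 0.546 with it.
- A separate 400-run check with baseline-dependent missing Day 60 values: rejection 3.8% and 4.3%. The Monte Carlo error is √(0.05 × 0.95 / 400), or 1.1 points, so these do not differ.

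**The case against.** A single baseline covariate is a valid, prespecified model, and it is stated consistently in both documents. The benefit of changing it may be zero. The slope depends on the SD ratio as well as the correlation: if the correlation falls from 0.7 to 0.5 while the SD grows 1.4-fold, the slope does not move (0.7 × 1.0 = 0.5 × 1.4).

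Design features also leave the pattern open. The study eye is the one with the higher staining score at randomization, and staining is graded visually. Regression to the mean from that selection would largely be present by Day 7 and carry through later visits, which favours a common slope. All subjects also take vehicle for 14 days before baseline. All of this stands, and it is why the point is conditional.

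A reader might infer more: that the model is known to under-adjust at Day 60, or that it biases the handling of missing Day 60 values. The documents support neither. Under-adjustment needs a slope that steepens over time, and no figure in the documents shows one. On missing data, the simulations show no bias. The unstructured covariance lets missing Day 60 values borrow from earlier visits, and the control-based imputation code already regresses each visit on baseline and prior visits with its own coefficients.

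The objection does not remove the asymmetry. With equal slopes the extra term moved the simulated SE by about 0.001; with unequal slopes it recovers precision.

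**Conclusion.** The point holds as an optional efficiency improvement. The primary model fits one baseline slope across four visits while testing only the last. If the slopes differ, Day 60 precision can be lost and a chance imbalance is only partly corrected, or over-corrected if the correlation rises. The size rests wholly on assumed correlations, with equal SDs across visits and site effects ignored: nothing with equal slopes, about 1% of variance with slight decay, 4 to 8% with moderate decay, and roughly 25% with steep decay. The calculations were scaled to tCFS; the same algebra applies to the symptom score.

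It would be wrong to read this as a flaw in validity or power. Randomization keeps the contrast unbiased on average, the model SE tracked the empirical SE in simulation, and rejection under the null stayed near 5%. The stated powers rest on an unadjusted t-test. In every tabled scenario the Day 60 residual SD under the shared slope stays below the planned 3.0; the largest is 2.697 in the exponential case (2.419 × √1.244).

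**What to change.** Before unmasking, add `baseline_value*visit` to the MODEL statement for both primary endpoints, and bring the model text in SAP 9.7.1 and 9.7.1.5.1 into line. In the ESTIMATE for the pooled SY-201 arm mean, add the matching baseline-by-visit coefficient: the overall baseline mean in the position of the visit being estimated, zero elsewhere. The ESTIMATE for the pooled difference from vehicle needs no change, because the baseline terms cancel.

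Record the addition in SAP 9.8.2 as a change from the protocol-specified model. If the sponsor prefers to keep the protocol model as primary, the same term can be prespecified as a sensitivity analysis.

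The cost is 3 model degrees of freedom (four slopes instead of one) with about 200 subjects, one extra ESTIMATE line, and a documented departure from the protocol text. No new data are needed.

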9.7.1. Statistical and Analytical Plans

General Conventions

Summary statistics for the data collected during this study will be presented to give a general description of the subjects studied. Data from all sites will be combined in the computation of these descriptive summaries. Categorical variables will be summarized by the frequency and percentage of subjects in each category. Continuous variables will be summarized using N, mean, standard deviation (SD), median, minimum, and maximum values.

Number of subjects, minimums, and maximums will be calculated to the same number of decimal places as the source data. Means, medians, standard deviations, and quartiles will be calculated to one more decimal place than the source data. Percentages will be calculated to the nearest one decimal place. Zero count cells will be displayed as "0" with percentage of (0%). Unless otherwise noted, summaries will be performed by the treatment group and presented in the order of: SY-201 2.0% or 1.0% or 0.5% (efficacy analyses only), SY-201, 2.0%; SY-201, 1.0%; SY-201, 0.5%; Vehicle.

Statistical tests will be presented as two-sided p-values rounded to four decimal places; p-values less than 0.0001 will be presented as '<0.0001' and p-values = 1 will be presented as '>0.9999' in all tables. Unless otherwise indicated, statistical testing will be carried out at the $\alpha = 0.05$ significance level.

Baseline values will be defined as the last measurement prior to dosing of double-masked study medication. Ocular measurements will use the most recent measurement for each eye.

Numeric laboratory data may be recorded at limits of detection (with a '<' or '>' sign, i.e. < 0.1 or > 0.1). To summarize the data, the original value will be converted to one unit less or more at the level of measured precision (e.g. 0.4 in the case of < 0.5 and to 0.6 in the case of > 0.5). The actual values will be presented in the data listings.

MMP-9 data may be recorded at limits of detection of < 5 ng/mL or > 1000 ng/mL. To summarize the data, the original value will be converted to either 4 ng/mL or 1010 ng/mL, respectively. The actual values will be presented in the data listings.

All data collected in this study will be presented in individual subject data listings for all subjects.

Computations for all results will be performed using SAS (Version 9.4, SAS/STAT 15.2) computer software package (SAS Institute, Inc, 2013, 2020), unless otherwise specified.

Strata and Covariates

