9.7.1.1.2. Analysis Eyes

Subjects in the FAS will have at least one eye that qualifies based on the criteria in the protocol. Both eyes may qualify based on the criteria.

Efficacy analyses will be performed in the study eye and non-study eyes.

The study eye is defined as the eye meeting all inclusion criteria and no exclusion criteria, and with the highest tCFS scoring at randomization (Visit 2, Day 1). If both eyes meet the inclusion criteria and no exclusion criteria and have the same tCFS score, the right eye will be used as the SE.

Safety analyses will be presented for both eyes.

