9.7.2. Determination of Sample Size

For mean change from baseline to Day 60 in tCFS, a sample size of 45 SY-201-treated subjects versus 45 vehicle-treated subjects will have 87.9% power to detect an effect size of 2.0 units with a standard deviation of 3.0 for an unpaired t-test with a 2-sided alpha = 0.05. For mean change from baseline to Day 60 in dry eye symptom , a sample size of 45 SY-201-treated subjects versus 45 vehicle-treated subjects will have 83.5% power to detect an effect size of 1.5 units with a standard deviation of 2.4 for an unpaired t-test with a 2-sided alpha = 0.05.

Fifty (50) subjects per treatment arm, for a total 200 subjects, will be enrolled to allow for some dropout of subjects.

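### LOCF and BOCF, two of the three planned sensitivity analyses, do not test the missing-at-random assumption by degree; a tipping-point analysis would, at small cost

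*SAP*

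**What the plan says.** The primary analysis (SAP 9.7.1.5.1) is a mixed model for repeated measures that treats missing scores as missing at random, whatever the reason. The same section, and the missing-data paragraph of SAP 9.7.1, list three sensitivity analyses of the primary endpoints: "control-based pattern imputation, last observation carried forward (LOCF), and baseline observation carried forward (BOCF". Sample code follows for the control-based imputation only. The public text gives no model, variance method or rule of interpretation for LOCF or BOCF.

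Two definitions affect what BOCF assumes. In SAP 9.7.1.1.2 the study eye is the qualifying eye "with the highest tCFS scoring at randomization (Visit 2, Day 1". In SAP 9.7.1, "Baseline values will be defined as the last measurement prior to dosing of double-masked study medication", which for tCFS is normally that same Visit 2 reading. Protocol 5.5.2 bars artificial tears during the run-in and supplies them as rescue in every arm from Visit 2 onward.

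On dropout, SAP 9.7.2 says only: "Fifty (50) subjects per treatment arm, for a total 200 subjects, will be enrolled to allow for some dropout of subjects". No rate by arm, reason or timing is given.

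**The concern.** A sensitivity analysis should show whether the Day 60 result survives plausible departures from MAR. BOCF sets every dropout's change to exactly zero. LOCF sets it to whatever was last seen. Neither can be made milder or harsher, so agreement with the primary result says little about how robust that result is.

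For tCFS, zero is also probably a poor guess. Choosing the worse of two noisy readings puts baseline above that eye's usual level, and rescue tears become available only after baseline. Some improvement is therefore likely in every arm without any drug effect, and BOCF denies it to dropouts. If vehicle loses more subjects, the contrast moves toward SY-201. Counting filled-in values as data also makes the standard error too small. BOCF could then look confirmatory partly because of who left the trial.

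**Working it through.** **The plan's own figures.** SAP 9.7.2 bases its power on a two-sided 5% t-test between two groups of equal size. For tCFS it says that "45 vehicle-treated subjects will have 87.9% power to detect an effect size of 2.0 units with a standard deviation of 3.0" when compared with as many on SY-201. For the symptom score, the same group sizes "will have 83.5% power to detect an effect size of 1.5 units with a standard deviation of 2.4". The noncentral t distribution gives 87.85% and 83.45%, so both reproduce. 45/(1 − 0.10) = 50, so the enrolment figure implies 10% dropout.

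**Inputs.** From the documents: N = 50 per arm and SD 3.0 for tCFS. Assumed, because the documents give no values: mean change m, the same in both arms (no drug effect); dropout dV = 15% on vehicle and dA = 5% on SY-201 (average 10%), random within arm.

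**Plausible size of m from worse-eye selection.** If each reading has error SD e and each eye's true score varies independently with SD t, the mean error in the eye that reads higher is e² / √(2(t² + e²)) × √(2/π).
- e = 1.0, t = 2.0: 1 / 3.162 × 0.798 = 0.25
- e = 1.5, t = 1.0: 2.25 / 2.550 × 0.798 = 0.70

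This gives roughly 0.3 to 0.7 units. Another assumed set (visit-to-visit SD 1 to 2, between-eye true-score correlation 0.8) gives 0.4 to 1.0. Both apply only to subjects with two qualifying eyes.

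**BOCF, closed form.**
- Difference, SY-201 minus vehicle: (1 − dA)m − (1 − dV)m = m(dV − dA). Negative favours SY-201.
- Variance per arm: (1 − d)(SD² + d·m²)/N.
- One-sided false significance, normal approximation: Φ(−1.96 + |difference|/SE).

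For m = −2.0: difference = −2.0 × 0.10 = −0.20. Variances are 0.85 × 9.6/50 = 0.1632 and 0.95 × 9.2/50 = 0.1748, so SE = √0.3380 = 0.581. Then Φ(−1.96 + 0.344) = 5.3%.

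| m | Difference | SE | False significance for SY-201 (nominal 2.5%) |
|---|---|---|---|
| −0.3 | −0.03 | 0.570 | 2.8% |
| −0.7 | −0.07 | 0.571 | 3.3% |
| −1.0 | −0.10 | 0.572 | 3.7% |
| −2.0 | −0.20 | 0.581 | 5.3% |

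Simulation of the t-test gives 2.7% and 3.4% for the first two rows and about 5.5% for the last. With dropout reversed (5% vehicle, 15% SY-201) the differences change sign, and at m = −2.0 false significance for SY-201 falls to 1.1%.

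**BOCF at the planned effect.** With changes of −3 on SY-201 and −1 on vehicle and 10% dropout in each, BOCF gives 0.9 × (−3) − 0.9 × (−1) = −1.8, which is conservative against −2.0. It overstates the effect only if dV × 1 > dA × 3, that is, if vehicle dropout exceeds three times SY-201 dropout.

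**LOCF.** The bias is the mean shortfall of the carried value times the dropout imbalance. Take the last visit as equally likely to be Day 7, 14 or 28.
- Steady improvement of −0.5, −1.0, −1.5, −2.0 at Days 7, 14, 28 and 60: the carried mean is −1.0, the shortfall is 1.0, and the bias is 1.0 × 0.10 = 0.10 units (false significance about 3.6%).
- Flat from Day 7: the shortfall is 0. Simulation at m = −0.3, −0.7 and −2.0 gives bias within 0.01 units and false significance of about 2.4%.
- A subject lost before Day 7 carries the baseline reading, so LOCF equals BOCF for that subject.

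**Standard error at 10% dropout in each arm.** Observed cases: √(2 × 9/45) = 0.632. BOCF with m = 0: √(2 × 0.9 × 9/50) = 0.569. BOCF with m = −2: √(2 × 0.9 × 9.4/50) = 0.582. No data were added.

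**The case against.** A reader might infer that the design makes both methods favour SY-201 and that false significance is about double the nominal rate. The documents do not support that. Regression to the mean shows in full at the first re-reading, so a carried Day 7, 14 or 28 score already includes it; LOCF bias needs continuing improvement, which no section describes. The 5% figure for BOCF needs a 2.0-unit improvement in every arm, well above what worse-eye selection yields. Rescue tears could add to that improvement, but the documents give no amount. The 15%/5% split is an assumption too, and the opposite split penalises the drug.

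The mechanism is also limited in reach. Worse-eye selection concerns tCFS only; the symptom score is recorded per subject. The 14-day vehicle run-in (Protocol 3.2) means vehicle subjects have no change of drop at Visit 2, though it cannot remove selection made at that visit. Sites try to obtain Visit 6 assessments from early leavers (Protocol 6.1, 6.2, 7.1.8), which should reduce missing data. Yet SAP 9.7.1.5 does not summarise early-termination data separately unless they fall in a scheduled window, and none is open on Days 31 to 56.

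The smaller standard error does not by itself raise false positives when dropout is equal, and the gap would be narrower against the repeated-measures model than against observed cases. Finally, these analyses sit outside the six-test hierarchy, and a control-based imputation is already planned.

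All of this stands, and it limits the size of the problem. It does not make LOCF or BOCF informative about departures from MAR.

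**Conclusion.** The concern holds as a modest weakness in the sensitivity plan. Two of the three analyses are single imputations that replace MAR with one fixed assumption, and only the control-based scenario is a principled alternative. Nothing in the readable plan shows how large a departure from MAR would remove Day 60 significance.

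For tCFS, BOCF is probably pessimistic for dropouts. Under the assumed 15%/5% split and no drug effect, the bias toward SY-201 is about 0.03 to 0.07 units if the common improvement is regression to the mean of 0.3 to 0.7 units, against a planned effect of 2.0. One-sided false significance is then about 2.7% to 3.4% against 2.5%. It is 0.20 units and about 5% only if all arms improve by 2.0 units. The sign depends on which arm loses more subjects. No direction can be stated for LOCF. The confirmatory type I error is unchanged. These sizes rest on assumed dropout, mean change and reading error, none of which the documents give.

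**What to change.** In SAP 9.7.1 (missing data) and 9.7.1.5.1:

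- Keep the control-based imputation.
- Replace LOCF and BOCF as evidence of robustness with a delta-adjusted multiple imputation. Impute under MAR within each arm, then worsen the imputed Day 60 values in the SY-201 arms in steps, for example 0 to 2.0 units for tCFS and 0 to 1.5 for the symptom score (the planned effects). Pool by Rubin's rules and report, for each comparison with vehicle, the penalty at which significance is lost.
- State what is reported if no tipping point is reached. At 10% missing, a 2.0-unit penalty moves the arm mean by only 0.10 × 2.0 = 0.20 units, so the upper end of the range may not overturn a clear result.
- If LOCF or BOCF is kept, label it descriptive.
- Set the imputation bounds to the score being imputed. The sample code caps values at 4, the maximum for one corneal sector, whereas total tCFS runs to 20.

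The cost is SAP wording and modest extra programming within the PROC MI approach already planned. The drawback is that the result is a range with a tipping point rather than one p-value.
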